11. STATISTICAL DATA ANALYSIS

11.1. Statistical analysis manager

The statistical analysis manager will be the trial statistician, based at UBx.

The statistical analysis plan will be written by the trial statistician and validated by the coordinating investigators.

11.2. Description of the statistical analysis plan

11.2.1. Analysis of the primary endpoint and algorithm validation

We will evaluate the proportion of missed TB cases in HIV-infected children with presumptive TB not initiated on treatment as per the PAANTHER TB treatment decision algorithm (i.e. false negative cases). We will then estimate the NPV (NPV=1-proportion of false negative) of the PAANTHER TB treatment decision algorithm and its 95% confidence interval. The NPV will be compared to the 75% minimal acceptable lower confidence interval limit.

The algorithm will be considered validated if its NPV remains significantly higher than 75% if the prevalence is at 50%, corresponding to a sensitivity significantly higher than 80%. If a lower diagnostic accuracy is found, we will update the existing prediction model and adjust or recalibrate it to the validation sample.

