An Endpoint Review Committee will be set up at the national level for the purpose of case review and validation of TB diagnosis. The national Endpoint Review Committee will review and validate all new TB cases in children initially non-treated for TB, using the updated Clinical Case Definitions for Classification of Intrathoracic Tuberculosis in Children (see Table 2). The Endpoint Review Committee will also validate differential clinical and other diagnoses on opportunistic infections and adverse events. All reviews will be performed following Standard Operating Procedures (SOPs) specifically developed for the study.

Additionally, at the international level, an Expert Committee will be set up for the purpose of clinical validation of TB diagnosis, including identification of children with unlikely TB in those initiated on treatment as per the PAANTHER TB treatment decision algorithm. The International Expert Committee will validate final TB diagnosis and will determine, based on timing, clinical features, and any other relevant information whether missed TB cases are false negatives, potential TB unmasking IRIS or new TB infections. The use of the updated Clinical Case Definitions for Classification of Intrathoracic Tuberculosis in Children will not be possible as treatment decision is not clinician based but algorithm-guided. The Expert Committee will also review part of all cases reviewed at country level to ensure homogeneity of classification across countries (See figure 2).

The Clinical Case Definitions for Classification of Intrathoracic Tuberculosis in Children were initially developed for children with suspected TB and may not be fully relevant for children with HIV infection [59]. They may be revised by the Scientific Advisory Board (SAB) based on current state of the art on time of final case review.

For the purpose of reference diagnosis and case definition, CXRs will be read by 2 independent experts experienced in reviewing CXRs in children, blinded to all of the clinical information and to each other's interpretation. In case of disagreement, advice from a third expert will be sought. For routine care, CXR will be read by the site clinician.

 Table 2. Updated Clinical Case Definitions for Classification of Intrathoracic Tuberculosis in

 Children (adapted from Graham et al, 2015 [59])

| Case definition | Refined criteria | | | |
|-----------------------------|---|--|--|--|

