4.2. Methodology

The PAANTHER algorithm was initially developed in two countries from South-East Asia (Cambodia, Vietnam) and two West African countries (Burkina Faso, Cameroon). To assess the algorithm's performance outside of its development settings, the study will be purposefully implemented in 4 different countries across Africa where TB incidence, HIV prevalence, patient mix and healthcare practices are likely to vary: Côte d'Ivoire, Uganda, Mozambique, and Zambia (Table 1).

The PAANTHER TB treatment decision algorithm will be used for a TB treatment decision by site clinicians in all children enrolled in the study. Validation of the algorithm will be performed by evaluating the proportion of missed TB cases in children not initiated on treatment as per the PAANTHER TB treatment decision algorithm. The safety of this strategy will be carefully assessed through review of safety reports every 4 to 6 months during study conduct by the IDMC.

Occurrence of algorithm failures in terms of missed TB cases (TB cases subsequently detected among untreated cases, i.e. false negatives) and cases with unlikely TB among those initiated on TB treatment as per the algorithm (cases not secondarily validated as confirmed or unconfirmed TB cases by the Expert Committee, i.e. false positives) will enable to estimate the negative and positive predictive values of the algorithm.

A centralized international Expert Committee will clinically review and validate TB diagnosis in children. This will enable assessment of the added value of new markers (MLR and CRP) and, if need be, to propose a new version of the score based on an optimised predicted probability.

• Study adaptation to the Covid-19 pandemic

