4.3. Sample size

Data obtained from the PAANTHER study showed that the TB prevalence was 57.3% in HIVinfected children with presumptive TB as defined per standard algorithm entry criteria, with a proportion of 39.3% of children being on ART. We expect a higher proportion of children on ART in this new study, reaching 50%, and a resulting lower prevalence of TB, around 50%, based on improved accesss to HIV care in our study settings.

With an algorithm sensitivity and specificity of 89% and 61%, respectively, the proportion of missed TB cases among children not started on treatment based on the PAANTHER algorithm (assessed by the TB incident cases in the 6 months period after applying the algorithm) is estimated to 15%, which corresponds to a negative predictive value (NPV) of 85%. For sample size calculations, we used this expected NPV of 85% and an unacceptable NPV of 75% (minimal acceptable 95% lower confidence interval limit), a one-sided test of level 5% and a probability β =5%, which results in a sample of 176 children not-initiated on treatment as per

the PAANTHER TB treatment decision algorithm and a total sample of 550 children, taking into account an expected 10% of missing data [63].

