6. STUDY INTERVENTIONS

6.1. Diagnostic procedure evaluated

The PAANTHER algorithm and prediction score was designed as a guiding tool for empirical TB treatment decision in HIV-infected children with presumptive TB (see Figure 1 below and Appendix 2). The proposed score includes:

- History of close contact with a smear+ TB case
- Suggestive TB symptoms (prolonged fever, unremitting cough, hemoptysis, weight loss in the past 4 weeks)
- Tachycardia
- Chest radiography features (miliary, alveolar opacities, lymph nodes)
- Abdominal ultrasound features (abdominal lymphadenopathy)
- Xpert MTB/RIF assay which will be replaced by Ultra

Points scored by each sign or symptom is shown in the table below.

| Exam/assessment | Features/items | Points | |
|----------------------|---|--------|--|
| Contact history | History of contact with a smear + TB case | 118 | |
| Symptoms | Fever lasting > 2 weeks | 66 | |
| | Unremitting cough | 39 | |
| | Hemoptysis in previous 4 weeks | 79 | |
| | Weight loss in previous 4 weeks | 24 | |
| Clinical signs | Tachyardia | 54 | |
| Xpert MTB/RIF Ultra | Positive Xpert MTB/RIF Ultra result | 241 | |
| Chest radiography | Miliary | 90 | |
| | Alveolar opacity | 74 | |
| | Lymph nodes | 100 | |
| Abdominal ultrasound | Abdominal lymph nodes | 73 | |

Table 4: PAANTHER TB treatment decision algorithm components and point scoring

[figure not shown]

Figure 1: Implementation of the PAANTHER TB treatment decision algorithm in the context of the TB-Speed study

A score of >100 is highly predictive of TB. In children with a score >100, anti-TB treatment will be initiated immediately. In children with a score of <100, TB treatment will not be initiated except in those with severe/life-threatening conditions for whom TB treatment decision could be made at the discretion of the site clinician. TB could be definitely ruled out after further assessment and decision made as to what treatment the children should receive in accordance with existing national protocols, along with clinical follow-up.

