7.5. TB treatment decision using the algorithm

As soon as possible and during clinical, biological and radiological investigations, the clinician will make a diagnosis according to the PAANTHER TB-treatment decision algorithm (see Figure 1). Alternative diagnoses will be collected. The diagnosis visit is expected at the latest at day 1 or 2.

A flexibility to start TB treatment in children with a score <100 will be allowed in case of severe/life threatening condition. Children without such conditions not started on TB treatment will be reevaluated at the day 7 visit.

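### Children scoring below 100 but treated at clinician discretion cannot count as missed TB, so the reported NPV may not be that of the algorithm and is likely, not certainly, too high

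*Protocol*

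**What the plan says.** - **The override.** Section 6.1: for scores below 100, "TB treatment will not be initiated except in those with severe/life-threatening conditions", where the decision is left to the site clinician. Section 7.5 repeats it: "A flexibility to start TB treatment in children with a score <100 will be allowed in case of severe/life threatening condition".
- **The endpoint.** Section 11.2.1 evaluates missed TB in children "not initiated on treatment as per the PAANTHER TB treatment decision algorithm (i.e. false negative cases") and sets "NPV=1-proportion of false negative". The result is called the NPV of the algorithm and is compared with 75%.
- **What counts as a miss.** Section 4.2: "TB cases subsequently detected among untreated cases, i.e. false negatives". Section 4.3: "assessed by the TB incident cases in the 6 months period after applying the algorithm".
- **Who reviews it.** Under section 3.3 the national committee is to "review and validate all new TB cases in children initially non-treated for TB". The same section has the international Expert Committee validate final TB diagnosis.
- **Derived measures.** Section 11.2.3 combines PPV and NPV to estimate sensitivity and specificity of the algorithm or scoring system. Its sensitivity analyses cover age, ART, CD4 count and nutritional status, with a separate look by country.
- **Flow chart.** A footnote in section 6.4 attaches the overridden children to one box of Figure 2, which is not visible in the text at hand.

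**The concern.** The primary endpoint is meant to measure how often the algorithm is wrong when it says not to treat. A child who scores below 100, has TB, and is treated on day 0 because of severity is an error of the algorithm. The clinician, not the score, prevented the consequence. Under the definitions in sections 4.2 and 4.3 that child cannot become a TB case detected later among the untreated, so the error goes unrecorded.

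The trial would then report the performance of the algorithm plus clinician rescue under the name of the algorithm. The 85% expected NPV was derived from the algorithm's own sensitivity and specificity, so benchmark and estimate would describe different things. Because sensitivity and specificity are back-calculated from NPV and PPV, the misclassification carries over to them.

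**Working it through.** **1. The plan's own figures.** Inputs from section 4.3: sensitivity 89%, specificity 61%, prevalence 50%, expected NPV 85%, unacceptable NPV 75%, one-sided 5%, β 5%, 10% missing data.

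- Share scoring negative = 0.50 × 0.11 + 0.50 × 0.61 = 0.36.
- NPV = 0.305 / 0.36 = 84.7%, which the protocol rounds to 85%. It applies to *all* algorithm-negatives.
- Exact binomial: n = 176, success at 142 or more without TB, gives one-sided error 4.6% at 75% and power 95.2% at 85%. The stated 176 is reproduced.
- Total: 176 / 0.36 = 489, and 489 / 0.90 = 544, against the stated 550.

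The sample size is not at fault.

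**2. Where the overridden child goes.** The phrase about not being initiated as per the algorithm has two readings.

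- *Untreated children.* The schedule in section 7.3 gives the day 7 visit only to those not initiated as per the algorithm. Section 7.5 describes that visit as being for children without severe conditions who were not started on treatment. Together with section 4.2 this leaves overridden children outside the primary group.
- *Children the algorithm says not to treat, whatever they received.* They stay in the denominator but, being treated, cannot be detected later among untreated cases. They count as not missed.

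**3. Formulas.** Let s be the share of algorithm-negatives overridden, q the TB share among them, and F the TB share among all algorithm-negatives.

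- Excluded: apparent NPV = 1 − (F − s·q)/(1 − s). This exceeds 1 − F only if q > F, that is, above 15% at design or 25% at the null.
- Kept as not missed: apparent NPV = 1 − F + s·q, too high for any q > 0.

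**4. Numbers.** F = 25% (true NPV exactly 75%). The values of s and q are assumptions. Under exclusion n falls to 176 × (1 − s), with exact pass marks of 135 of 167 and 128 of 158.

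| s | q | Apparent NPV, excluded | False validation | Apparent NPV, kept as not missed | False validation |
|---|---|---|---|---|---|
| 5% | 40% | 1 − 0.230/0.95 = 75.8% | 7.3% | 77.0% | 14.1% |
| 5% | 60% | 1 − 0.220/0.95 = 76.8% | 12.8% | 78.0% | 22.3% |
| 10% | 40% | 1 − 0.210/0.90 = 76.7% | 11.4% | 79.0% | 33.0% |
| 10% | 60% | 1 − 0.190/0.90 = 78.9% | 29.3% | 81.0% | 58.8% |

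The reference error rate is 4.6%. Under exclusion with q = 25% the bias is zero. With s = 10% and q = 15% the apparent NPV is 1 − 0.235/0.90 = 73.9%, a downward bias.

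**The case against.** **The aim is safety of withholding.** Section 1 describes a management study of withholding treatment and exempts severe children in the same sentence; section 6.1 writes the exemption into the decision rule. An untreated-only NPV answers that question. This stands as a reason to keep that measure, but not to label it the NPV of the algorithm or to derive sensitivity and specificity from it.

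**The override is about severity, not TB suspicion.** By Table 4, a final score below 100 rules out a positive Ultra result (241 points) and a smear-positive contact (118 points). This stands in part. A TB share above 15-25% is plausible where a clinician chose TB treatment and expected prevalence is about 50%, but the documents do not establish it.

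**The Expert Committee's remit is wider.** Sections 3.3 and 13.5 let it validate final TB diagnosis without restriction to untreated children, and Figure 2 may place the overridden group. So a reader who infers that their TB can never be recognised goes too far. Still, no rule in sections 11.2.1 to 11.2.3 carries such a diagnosis into the NPV.

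**This belongs in the SAP.** Section 11.2.3 defers detail on secondary endpoints. The primary endpoint, the definition of a miss and the pass rule are fixed in the protocol.

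**Conclusion.** The point holds as a misclassification built into the stated definitions. Under neither reading can an overridden child with TB count as a miss, while the result is presented as accuracy of the algorithm. If these children are kept as not missed, the bias is upward for any TB share above zero. If they are excluded, it is likely but not certainly upward. The size rests wholly on assumed override and TB shares: under exclusion at a true NPV of 75%, the error rate goes from 4.6% to 7-13% with 5% overridden and to 11-29% with 10% overridden.

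Two stronger inferences are not supported.

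- *Loss of power.* This follows only if the 85% is assigned to the untreated alone. Section 4.3 derives it for all algorithm-negatives. With that 85%, s = 10% and q = 50%, the untreated NPV is 1 − (0.15 − 0.05)/0.90 = 88.9%, and exact power at n = 158 is 99.9%.
- *A by-score NPV below the pass mark of 142/176 = 80.7%.* This needs the same reassignment. Even then, with 178 negatives, 9, 18 or 27 overridden and 30% or 50% TB among them, only one of the six combinations falls below it, at 79.7%, which is still above the unacceptable 75%.

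**What to change.** 1. Define the algorithm NPV and every 2x2 accuracy table by final score, not by treatment received.
2. Keep overridden children with a final score below 100 as algorithm-negative, with TB status from the Expert Committee, and keep them out of the PPV denominator.
3. Scoring runs from day 0 to day 2, while the flow-chart footnote places the override at day 0. Classify by final score any child whose score later exceeds the cut, and report children with incomplete scoring separately.
4. Report the untreated-only NPV alongside as the safety-of-withholding measure, and give bounds counting all or none of the overridden children as missed.

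The cost is protocol and SAP wording and a flag in the eCRF; no visit or sample is added. The downsides are that TB status in overridden children is judged while they are on treatment, and that the NPV may be slightly less favourable. No change to the clinical override is implied.

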11.2.2. Intermediate analyses

Intermediate analyses will be performed every 4 to 6 months and submitted confidentially to the IDMC (see chapter 13.2). These will include the proportion of missed TB cases in the group of children not initiated on TB treatment as per the PAANTHER TB treatment decision

algorithm, as well as global morbidity and mortality data in this group. The first intermediate analysis will be performed after 4 months of enrolment. The timing of the following intermediate analyses will be decided with the IDMC.

11.2.3. Analysis of secondary endpoints

The median time to TB treatment decision and interquartile range, and the proportion of children with presumptive TB having completed the PAANTHER TB treatment decision algorithm will be estimated.

We will assess the proportion of HIV-infected children with unlikely TB among those initiated on treatment as per the PAANTHER TB treatment decision algorithm (false positive cases) identified by the international Expert Committee. We will estimate the positive predictive value (PPV) and its 95% confidence intervall. Once PPV and NPV are assessed, we will estimate sensitivity and specificity of the algorithm/scoring system and TB prevalence.

Discrimination and calibration, which are key measures of a model's predictive performance, will be quantified for the original model and the model incorporating new predictors. To avoid adding optimism, the original model will not be redeveloped. Discrimination of the model, measured by the C statistic, or area under the receiver operating characteristic (AUROC) curve, will be estimated for the original model and parameters with and without potential new predictors such as MLR and CRP. AUCs of the models will be compared using bootstrapping technique. Calibration examines the agreement between predicted and observed risk of disease and can be quantified by a calibration slope and the expected/observed (E/O) statistic (ratio of the total expected to have disease to the total observed with disease). TB diagnosis as assessed through the Expert Committee review of false negative and false positive cases will be used as reference standard.

Sensitivity analyses will be conducted to assess impact of age, ART, CD4, and nutritional status on the performance of the score. Furthermore, the score will be assessed country-wise to identify potential heterogeneity in score performances between countries.

If a lower predictive accuracy is found, we will update the existing prediction model and adjust or recalibrate it to the validation sample. As a result, the updated model combining the information from the original PAANTHER model with new information from the TB-Speed study, will probably have improved transportability to other populations.

Sensitivity, specificity, and predictive values of Ultra in NPA and stool will be measured for each specimen independently and for the combination of the 2 specimens against mycobacterial culture.

Analysis of secondary endpoints will be further detailed in the statistical analysis plan.

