2.2. Secondary objectives

- 1. To evaluate the feasibility of the PAANTHER TB treatment decision algorithm in HIVinfected children with presumptive TB
- 2. To assess the proportion of HIV-infected children with unlikely TB among those initiated on treatment as per the PAANTHER TB treatment decision algorithm
- 3. In HIV-infected children with presumptive TB, including comparison of those initiated and those not initiated on TB treatment as per the PAANTHER TB treatment decision algorithm, to assess:
 - a. Incidence of morbidity (drug toxicity, opportunistic infections, IRIS) and mortality during 6 months after enrolment
 - b. Time to ART initiation in those who are ART-naïve
 - c. Immunologic evolution at 6 months after enrolment
- 4. To assess TB treatment outcomes in HIV-infected children initiated on treatment as per the PAANTHER TB treatment decision algorithm
- 5. To assess the feasibility of IPT initiation in HIV-infected children not initiated on treatment as per the PAANTHER TB treatment decision algorithm
- 6. To assess the performance of the MLR and the C-reactive protein (CRP) and their potential added value in the PAANTHER score and algorithm to detect TB
- 7. To evaluate the diagnostic performance of Ultra performed on one NPA and one stool sample against mycobacterial culture performed on standard samples (GA in younger children or expectorated sputum in older children) in HIV-infected children
- 8. To assess the feasibility of stool sample collection, and the feasibility, safety, and tolerability of NPA collection in HIV-infected children
- 9. To assess the performance of the PAANTHER algorithm for TB diagnosis across various ages, CD4 counts, nutritional statuses, and timings of ART initiation
- 10. To evaluate the cost effectiveness of implementing the PAANTHER TB treatment decision algorithm compared to the estimated effect of the standard of care in children with HIV

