3.2. Secondary study endpoints

1. Time to final TB treatment decision and proportion of children with presumptive TB having completed the PAANTHER TB-treatment decision algorithm

The algorithm will be considered completed if a decision to initiate TB treatment has been taken at any step of the algorithm or if TB has been excluded after systematic evaluation, and all steps planned in the algorithm have been implemented.

 Proportion of cases considered as unlikely TB by the Expert Committee in those initiated on treatment as per the PAANTHER TB treatment decision algorithm (false positive) 3.

- a. Morbidity (drug-induced toxicity ART and TB treatment-related, opportunistic infections, IRIS), with or without TB treatment, and mortality at 6 months
- b. Time to ART initiation in ART-naïve children
- c. CD4 (absolute count and %) gain
- 4. Weight gain at 6 months (absolute value and percentage of body weight), TB symptoms resolution and outcomes in children on TB treatment
- 5. Time to IPT initiation and proportion of children initiated on IPT in those not initiated on treatment as per PAANTHER TB treatment decision algorithm
- Discrimination (area under the receiver-operating-characteristic curves [AUROC]) and calibration measures of the PAANTHER prediction model including or not MLR and CRP, against the TB composite reference standard as defined by the Expert Committee
- 7. Proportion of NPAs (or sputum) and stool samples with *mycobacterium tuberculosis* (MTB) detected using Ultra
- 8. Feasibility defined as proportion of children with NPA and stool samples collected as per study protocol

Safety defined as proportion of NPA with AEs (vomiting, nose bleeding, low oxygen saturation, respiratory distress) occurring during NPA and

Tolerability defined as discomfort/pain/distress experienced by the child during NPA as assessed by the child (Wong-Baker face scale), by the parents (visual analog scale), by the nurses (FLACC behavioral scale) (quantitative assessment) in a subset of children

- Diagnostic accuracy (false negative and false positive rates i.e. NPV and PPV and corresponding sensitivity and positivity) of the PAANTHER algorithm in the different subgroups in terms of age, CD4 counts, nutritional statuses, and timings of ART initiation (on/off ART)
- 10. Incremental cost-effectiveness ratio (ICER)

3.3. Reference diagnosis/case definitions and validation by the Endpoint Review Committee and the international Expert Committee

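### Read as a significance test, the bootstrap comparison of AUCs with and without MLR and CRP does not hold its level, because the models are nested and the new weights are fitted in the same data

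*Protocol*

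**What the plan says.** Protocol section 2.2, objective 6, is "To assess the performance of the MLR and the C-reactive protein (CRP) and their potential added value in the PAANTHER score and algorithm to detect" (the target condition being TB). Section 3.2, endpoint 6, is discrimination (AUROC) together with "calibration measures of the PAANTHER prediction model including or not MLR and CRP, against the TB composite reference standard as defined by the Expert Committee".

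Section 11.2.3 gives the method. The AUROC "will be estimated for the original model and parameters with and without potential new predictors such as MLR and CRP", and then "AUCs of the models will be compared using bootstrapping technique". Calibration is to be quantified for both models, but no comparison of it is named, and no test of the MLR or CRP coefficients appears. The same section protects the original score: "To avoid adding optimism, the original model will not be redeveloped". It closes with "Analysis of secondary endpoints will be further detailed in the statistical analysis plan".

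The protocol does not state the resampling scheme, interval type, test level or criterion for added value.

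**The concern.** The larger model is the PAANTHER model plus two terms, so the models are nested. Table 4 (section 6.1) gives points for every existing item and none for MLR or CRP. Their weights can only come from the TB-Speed data, so the larger model is not a score fixed in advance.

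A bootstrap of the AUC difference behaves well for two pre-specified scores that differ. Here, if the markers add nothing, their fitted coefficients go towards zero, the two scores coincide, and the AUC difference collapses to a small, mostly positive quantity that is far from normal. Bootstrap limits then do not give a 5% test. The direction of the error depends on whether the model is refitted in each resample and on how the limits are formed.

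A smaller point concerns optimism. The original score is evaluated with fixed weights, while the extended model is fitted and evaluated in the same children, so only one side of the comparison carries optimism.

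At stake is the answer to objective 6: a modest real marker may be reported as adding nothing, or a null pair may be flagged too often.

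**Working it through.** **Plan's own figures.** The protocol gives no level, power or effect size for this comparison, so there is nothing to reproduce on this point. The primary sample size (section 4.3) does reproduce. An exact binomial test of NPV 85% against 75%, one-sided 5%, first reaches 95% power at 176 (power 0.9525). The algorithm-negative share is 0.5 × 0.11 + 0.5 × 0.61 = 0.36, so 176 / 0.36 = 489 and 489 / 0.90 ≈ 544, close to the stated 550.

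**Inputs from the protocol.**
- Size: "a total sample of 550 children, taking into account an expected 10% of missing data", so 550 × 0.90 = 495 complete.
- TB prevalence: 50% (section 4.3).
- Sensitivity 88.6% and specificity 61.2% in the development study (section 1).

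**Assumed inputs.** The protocol gives neither a base AUC nor marker effects.
- Setting A: the operating point above under an equal-variance binormal model. d' = z(0.886) + z(0.612) = 1.206 + 0.285 = 1.49, so AUC = Φ(1.49/√2) = 0.854.
- Setting B: base AUC 0.80, so d' = √2 × z(0.80) = 1.19.
- Markers: normal, independent of the score, shifted by a stated number of SDs in children with TB.

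**True AUC gain.** For independent markers the new d' is √(d'² + sum of squared shifts).
- A, both markers at 0.25 SD: √(2.220 + 0.125) = 1.531. The gain is 0.0066.
- A, one marker at 0.5 SD: √(2.220 + 0.25) = 1.572. The gain is 0.013.
- B, one marker at 0.3, 0.4 or 0.6 SD: gains of 0.007, 0.013 and 0.027.

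**Simulated rejection rates** (two markers in the model, nominal two-sided 5%, 200 resamples, 300 to 1,000 replicates):

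| Setting | Likelihood-ratio | Fixed predictions | Refit, Wald | Refit, percentile |
|---|---|---|---|---|
| A, n=495, no effect | 5.4% | 0.2% | 0.0% | 8.5% |
| A, n=495, both at 0.25 SD | 80% | 24–25% | 20% | 77% |
| A, n=495, both at 0.30 SD | 94% | 42–46% | 36% | 90% |
| B, n=550, no effect | 3.6% | 0.0% | 0.0% | 7.4% |
| B, n=550, one at 0.2 SD | 42% | 7–8% | 5% | 42% |
| B, n=550, one at 0.3 SD | 79% | 23–27% | 19% | 77% |
| B, n=550, one at 0.4 SD | 97% | 53–57% | 50% | 96% |
| B, n=550, one at 0.6 SD | 100% | 97% | 97% | 100% |

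The fixed-prediction range covers Wald and percentile limits.

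A separate run of setting A agreed. Under no effect it gave 5.7% for the likelihood-ratio test, 0.3–1.0% for fixed predictions, 0% for refit Wald and 8.7% for refit percentile. At 0.25 SD in both markers, power was 82% for the likelihood-ratio test, 19–27% for the fixed and Wald forms, and 76% for refit percentile. With one marker at 0.5 SD the conservative forms reached 62–70%.

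With a single marker in the model (B, n=550), refit percentile rejects 1.8% under no effect. At 0.3 SD its power is 63% against 85% for the likelihood-ratio test. Its error therefore changes direction with the number of markers.

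**Optimism.** The mean apparent AUC gain under no effect is about +0.001 in A and +0.0015 in B with two markers.

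**The case against.** The strongest reply is that the protocol states an estimate, not a test. Endpoint 6 is AUROC and calibration with and without the markers, and comparing AUCs addresses that directly. No null hypothesis, level or decision rule is given, and the choice of bootstrap can properly be left to the SAP. This stands in part: as description, the AUC comparison is legitimate, and an unstated scheme is not in itself a fault. It does not dispose of the point. The protocol has already chosen the AUC comparison as the only one between models, and further detail in the SAP would not turn it into a valid test of nested models.

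Three stronger readings are tempting and not supported.
- A reader might infer that the comparison almost never rejects. That is true under no effect and for weak markers. It is not true for strong ones (97% at 0.6 SD), nor for refit with percentile limits, which the wording allows.
- A reader might infer that a useful marker will probably be missed. The large shortfall is for true AUC gains below about 0.01, and whether such a gain is useful is open.
- A reader might infer that the decision to propose a new score hangs on this p-value. Section 4.2 mentions a new version only if needed, and section 11.2 ties updating to a finding of lower accuracy. Neither cites this comparison.

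The base AUC, the marker effects and their independence from the score are assumptions. A small run (40 replicates) at base AUC 0.75 and 0.85 showed the same pattern.

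**Conclusion.** The point holds in a limited form. If the bootstrap AUC comparison is used to decide whether MLR and CRP add value, none of the forms simulated holds 5% with two markers: fixed-prediction and Wald forms give 0 to 1%, and refit percentile gives about 7 to 9%. At effects where a likelihood-ratio test has about 80% power, the bootstrap has anywhere from about 20% to 77%, depending on a choice the protocol leaves open. The optimism in the apparent gain is real but small.

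These sizes rest on 495 to 550 children, 50% prevalence, base AUC 0.80 to 0.85, and two normal markers independent of the score. Only one secondary objective is affected.

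**What to change.** In section 11.2.3, replace the sentence on comparing AUCs with wording to this effect: the added value of MLR and CRP will be tested by a likelihood-ratio test of their coefficients in a logistic model that contains the original PAANTHER linear predictor. The change in AUROC will be reported as the measure of added value, corrected for optimism by refitting in each bootstrap sample and evaluating in the original sample. It will not serve as the significance test.

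The last clause matters because the optimism-corrected difference used as a Wald test is more conservative still: 7% power at 0.3 SD in setting B, against 79% for the likelihood-ratio test.

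The change needs a few lines of wording and no new data, keeps the original score fixed, and still delivers endpoint 6. The downside is that a clinically unimportant gain may reach significance, so the size of the AUROC change must be read alongside the test.
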